5.4.4. Rash/Hypersensitivity Stopping Criteria

A subject presenting with a Grade 3 AE or higher rash (diffuse macular, maculopapular, OR morbilliform rash with vesicles or limited number of bullae; OR superficial ulcerations of mucous membrane limited to 1 site) or a Grade 2 rash (diffuse macular, maculopapular, or morbilliform rash; OR target lesions) with evidence of systemic involvement will be followed as appropriate until resolution of the AE(s).

5.5. Subject and Study Completion

A completed subject is one who has completed all phases of the study including the Follow-up Visit.

The end of the study is defined as the last subject's last visit.

6. STUDY TREATMENT

6.1. Investigational Product and Other Study Treatment

The term "study treatment" is used throughout the protocol to describe any combination of products received by the subject as per the protocol design. Study treatment may, therefore, refer to the individual study treatments or the combination of those study treatments.

	Study Treatment
Product name:	Gepotidacin (GSK2140944)
Dosage form:	IV
Unit dose strength/Dosage level:	750 mg
Route of Administration/Duration	Single IV dose over 2 hours
Dosing instructions:	Instructions for the preparation of the IV drug are included in the Study Procedures Manual.
Physical description:	Gepotidacin lyophile is a pale yellow to greyish yellow cake. Reconstituted solution: A clear, dark brown to dark brownish-yellow solution after reconstitution, free from visible particulate matter.
Manufacturer/Source of procurement:	GlaxoSmithKline

6.2. Treatment Assignment

This is a nonrandomized, open-label study. Clinic personnel will enroll the subject into the study once a subject has met all eligibility requirements.

At Screening, subjects will be enrolled to the appropriate groups based on the classification as defined in the FDA draft guidance for industry, "Pharmacokinetics in Patients with Impaired Renal Function – Study Design, Data Analysis, and Impact on Dosing and Labeling" [DHHS, 2010].

Subjects with normal renal function and subjects with renal impairment (or ESRD) will be assigned to a study group based on their eGFR calculated using the isotope dilution mass spectrometry-traceable Modification of Diet in Renal Disease formula as follows:

- $eGFR \text{ (mL/min/1.73 m}^2\text{)} = 175 \times (\text{serum creatinine}) - 1.154 \times (\text{age}) - 0.203 \times (0.742 \text{ if female}) \times (1.212 \text{ if African American})$

In addition, subjects with normal renal function will be classified based on estimated Cl_{cr} by the Cockcroft-Gault equation.

Cl_{cr} in mL/min is estimated from a spot serum creatinine (mg/dL) determination using the following formula:

- $Cl_{cr} \text{ (mL/min)} = [140 - \text{age (years)}] \times \text{weight (kg)} \div 72 \times \text{serum creatinine (mg/dL)} (\times 0.85 \text{ for female patients})$

Subjects will be given a subject number that will be a unique identifier. Once a subject number has been assigned, the number will not be reused even if the subject withdraws from the study before receiving gepotidacin.

6.3. Planned Dose Adjustments

Planned dose adjustments are not allowed during this study. However, based on emerging data from Part 1 (or Period 1 for Group F), the Part 2 (or Period 2 for Group F) dose may be reduced.

6.4. Blinding

This will be an open-label study.

6.5. Packaging and Labeling

The contents of the label will be in accordance with all applicable regulatory requirements.

6.6. Preparation/Handling/Storage/Accountability

A description of the methods and materials required for the preparation of gepotidacin will be detailed in a Study Specific Technical Agreement/Memo or pharmacy manual which will be accompanied by a Quality Agreement.

- The investigator or designee must confirm appropriate temperature conditions have been maintained during transit for all study treatment received and any discrepancies are to be reported and resolved before use of the study treatment.
- Only subjects enrolled in the study may receive study treatment and only authorized clinic staff may supply or administer study treatment. All study treatments must be stored in a secure environmentally controlled and monitored (manual or automated) area in accordance with the labelled storage conditions with access limited to the investigator and authorized clinic staff.

- The investigator, institution, or the head of the medical institution (where applicable) is responsible for study treatment accountability, reconciliation, and record maintenance (i.e., receipt, reconciliation, and final disposition records).
- Further guidance and information for final disposition of unused study treatment are provided in the Study Reference Manual (SRM).
- Under normal conditions of handling and administration, study treatment is not expected to pose significant safety risks to clinic staff.
- A Material Safety Data Sheet or equivalent document describing occupational hazards and recommended handling precautions either will be provided to the investigator, where this is required by local laws, or is available upon request from GSK.

6.7. Compliance with Study Treatment Administration

When subjects are dosed at the clinic, they will receive study treatment directly from the investigator or designee, under medical supervision. The date and time of each dose administered in the clinic will be recorded in the source documents. The dose of study treatment and study subject identification will be confirmed at the time of dosing by a member of the clinic staff other than the person administering the study treatment.

Gepotidacin will be administered IV to subjects at the clinic. Administration will be documented in the source documents and reported in the electronic case report form (eCRF).

6.8. Treatment of Study Treatment Overdose

Gepotidacin will be administered at the clinic, thus limiting the risk of overdose. In the unlikely event that an overdose with gepotidacin should occur, the investigator must notify the sponsor promptly. There is no specific antidote for overdose with a bacterial topoisomerase inhibitor such as gepotidacin. In the event of a suspected overdose, it is recommended that the appropriate supportive clinical care should be instituted, as dictated by the subject's clinical status.

GSK does not recommend specific treatment for an overdose.

In the event of an overdose the investigator should:

1. Contact the medical monitor immediately
2. Closely monitor the subject for AEs/SAEs and laboratory abnormalities until gepotidacin can no longer be detected systemically (at least 3 days for gepotidacin)
3. Obtain a plasma sample for PK analysis within 3 days from the date of the last dose of study treatment if requested by the medical monitor (determined on a case-by-case basis)
4. Document the quantity of the excess dose as well as the duration of the overdosing in the eCRF

Decisions regarding dose interruptions or modifications will be made by the investigator in consultation with the medical monitor based on a clinical evaluation of the subject.

6.9. Treatment after the End of the Study

Subjects will not receive any additional treatment from GSK after completion of the study because only healthy subjects; subjects with mild, moderate, and severe renal impairment; and subjects with ESRD are eligible for study participation.

The investigator is responsible for ensuring that consideration has been given to the post-study care of the subject's medical condition, whether or not GSK is providing specific post-study treatment.

6.10. Lifestyle and/or Dietary Restrictions

6.10.1. Meals and Dietary Restrictions

Standard meals will be provided during the study dosing period at specified times.

Subjects will refrain from consumption of red wine, Seville oranges, grapefruit or grapefruit juice, pummelos, pomegranate juice, exotic citrus fruits, grapefruit hybrids, or fruit juices from 7 days prior to the first dose of study medication until after the final dose.

6.10.2. Caffeine and Alcohol

- Subjects will abstain from ingesting caffeine- or xanthine-containing products (e.g., coffee, tea, cola drinks, and chocolate) for 24 hours prior to the start of dosing until collection of the final PK sample.
- During each dosing session, subjects will abstain from alcohol for 24 hours prior to the start of dosing until collection of the final PK sample.

6.10.3. Activity

Subjects will abstain from strenuous exercise for 48 hours prior to each blood collection for clinical laboratory tests. Subjects may participate in light recreational activities during the study (e.g., watch television, read).

6.11. Concomitant Medications and Non-Drug Therapies

6.11.1. Permitted Medications and Non-Drug Therapies

In subjects with normal renal function, acetaminophen at doses of ≤ 2 grams/day is permitted; and in subjects with renal impairment or ESRD, acetaminophen at doses of ≤ 2 grams/day is permitted for use with the approval of the investigator. Other concomitant medication may be considered on a case-by-case basis by the investigator in consultation with the medical monitor.

Subjects with renal impairment and subjects with ESRD may be taking medications that are considered therapeutic, and these medications should not interfere with the conduct of the study. Subjects with renal impairment should be on a stable regimen of chronic medications 7 days before the first dose of study drug on Day 1 until completion of the Follow-up Visit.

All concomitant medication use will be documented on the concomitant medication page in the eCRF.

6.11.2. Prohibited Medications and Nondrug Therapies

Subjects with normal renal function, subjects with renal impairment, and subjects with ESRD must abstain from taking prescription or nonprescription drugs (including vitamins and dietary or herbal supplements), unless specified in Section 6.11.1, within 7 days (or 14 days if the drug is a potential enzyme inducer) or 5 half-lives (whichever is longer) prior to the first dose of study medication until completion of the Follow-up Visit, unless, in the opinion of the investigator and Sponsor, the medication will not interfere with the study.

Due to the potential for acetylcholinesterase inhibition with gepotidacin, the following medications are prohibited:

- Succinylcholine or other depolarizing muscle relaxants.
- Acetylcholinesterase inhibitors as required for myasthenia gravis including edrophonium, pyridostigmine, neostigmine, etc.

7. STUDY ASSESSMENTS AND PROCEDURES

Protocol waivers or exemptions are not allowed with the exception of immediate safety concerns. Therefore, adherence to the study design requirements, including those specified in the Time and Events Tables are essential and required for study conduct.

This section lists the procedures and parameters of each planned study assessment. The exact timing of each assessment is listed in the Time and Events Tables, Section 7.1.

The following points must be noted:

- If assessments are scheduled for the same nominal time, THEN the assessments should occur in the following order:
 1. 12-lead ECG
 2. vital signs
 3. blood draws

Note: The timing of the assessments should allow the blood draw to occur at the exact nominal time.

- The timing and number of planned study assessments, including safety and PK assessments, may be altered during the course of the study based on newly available

data (e.g., to obtain data closer to the time of peak plasma concentrations) to ensure appropriate monitoring.

- The change in timing or addition of time points for any planned study assessments must be documented in a Note to File which will be approved by the relevant GSK study team member and then archived in the study sponsor and clinic study files, but this will not constitute a protocol amendment.
- The institutional review board (IRB)/independent ethics committee (IEC) will be informed of any safety issues that require alteration of the safety monitoring scheme or amendment of the informed consent form (ICF).
- No more than 500 mL of blood will be collected over the duration of the study, including any extra assessments that may be required.

7.1. Time and Events Tables

Table 2 Time and Events Table (Groups A, B, C, D, and E)

Procedure	Screening (up to 30 days prior to Day -1)	Check-in	Treatment Period (Days)			Follow-up (10 [\pm 5] days post-last dose) or Early Termination	Notes
		-1	1	2	3		
Confined to clinic		X	X	X	X		Subjects will be admitted to the clinic on Day -1 and will be discharged on Day 3. Confinement will be 4 days and 3 overnight stays
Informed consent	X						
Inclusion and exclusion criteria	X	X					
Demographics	X						
Complete physical examination including height and weight	X						
Abbreviated physical examination		X			X	X	
Medical history (includes substance usage and history of renal disease)	X						Substances: drugs, alcohol, and caffeine. Subjects with renal impairment should be on a stable regimen of chronic medications 7 days before the first dose of study drug on Day 1.
Past and current medical conditions (including renal impairment medical history and eGFR)	X						eGFR as defined in the FDA draft guidance for industry, "Pharmacokinetics in Patients with Impaired Renal Function" [DHHS, 2010]. Subjects with normal renal function will also be classified based on Cl _{cr} .
Serum or urine pregnancy test/FSH	X	X				X	Serum (or urine) pregnancy test (if WCBP); estradiol and FSH at Screening, as appropriate
HIV antibody, hepatitis B surface antigen, and hepatitis C antibody testing ^a	X						
Drug and alcohol screen	X	X					See Table 6 .

Procedure	Screening (up to 30 days prior to Day -1)	Check-in	Treatment Period (Days)			Follow-up (10 [±5] days post-last dose) or Early Termination	Notes
		-1	1	2	3		
Laboratory assessments (include liver chemistries)	X	X		X		X	Including serum chemistry, hematology and urinalysis. Results from 24 hours after dosing should be available before discharge on Day 3.
12-lead ECG	X	X	X	X	X	X	
Vital signs	X	X	X	X	X	X	Respiratory rate and body temperature collected at Screening only.
Genetic sample ^b		X					Collect a pharmacogenomics (PGx) sample only if the subject has a signed consent specific for this purpose. The PGx sample can be collected anytime, but Day -1 is recommended.
Study drug administration			X				
Blood collection for pharmacokinetics			X	X	X		See Table 3 for time points.
Urine collection for pharmacokinetics			X	X	X		Subjects with normal renal function and subjects with renal impairment will have different collection intervals. See Table 3 for time points.
Saliva collection for pharmacokinetics ^c			X	X	X		See Table 3 for time points.
AE/SAE review	X	X	←-----→			X	
Concomitant medication review		X	←-----→			X	

AE = adverse event, Clcr = estimated creatinine clearance; eGFR = estimated glomerular filtration rate, ECG = electrocardiogram, FSH = follicle stimulating hormone; HIV = human immunodeficiency virus; PGx = pharmacogenetic, SAE = serious AE; WCBP = women of childbearing potential.

- a If test has otherwise been performed within 3 months before the first dose of study treatment, testing at Screening is not required.
- b Informed consent for optional substudies (e.g., genetics research) must be obtained before collecting a sample.
- c Subjects in Part 1 only. It should be noted that subjects with renal impairment may be on medications that may prevent saliva collections.

Table 3 Safety and PK Assessments (Groups A, B, C, D, and E)

Procedure ^a	Predose	Treatment Period Time point (hours)														
		0	0.25	0.5	1	1.5	2	2.5	3	4	6	8	12	24 ^b	36 ^b	48 ^b
12-lead electrocardiogram	X					X	X			X		X	X	X	X	X
Vital signs	X					X	X			X		X	X	X	X	X
Treatment administration 2-hour IV gepotidacin infusion		X														
Blood collection for pharmacokinetics	X		X	X	X	X	X	X	X	X	X	X	X	X	X	X
Urine collection for pharmacokinetics (subjects with normal renal function) ^c	X	X					X			X	X	X	X	X	X	
Urine collection for pharmacokinetics (subjects with renal impairment) ^d	X	X								X		X	X	X	X	
Saliva collections ^e	X		X	X	X	X	X	X	X	X	X	X	X	X	X	X

^a When coinciding with safety and/or pharmacokinetic assessments, electrocardiograms, vital signs, and pharmacokinetic blood collections should be performed in said order.

^b The 24-, 36-, and 48-hour postdose time points correspond to time points on Day 2 and 3, respectively.

^c Urine collection intervals for subjects with normal renal function (Group A and Group D) include 0 (pre-dose), 0 to 2 hours, 2 to 4 hours, 4 to 6 hours, 6 to 8 hours, 8 to 12 hours, 12 to 24 hours, 24 to 36 hours, and 36 to 48 hours.

^d Urine collection intervals for subjects with renal impairment (Group B, Group C, and Group E) include 0 hour (pre-dose), 0 to 6 hours, 6 to 12 hours, 12 to 24 hours, 24 to 36, and 36 to 48 hours.

^e Subjects in Part 1 only. It should be noted that subjects with renal impairment may be on medications that may prevent saliva collections.

Table 4 Time and Events Tables (Group F)

Procedure ^a	Screening (up to 30 days prior to Day -1)	Check -in	Treatment Period (Days)								Follow-up (10 [±5] days post-last dose) or Early Termination	Notes
			1				2					
			-1	1	2	3	4 to 6	7	8	9		
Confined to clinic ^b		X	X	X	X		X	X	X	X		Subjects will be admitted to the clinic on Day -1 and Day 7, and will be discharged on Day 3 (Period 1) and Day 10 (Period 2). Confinement will be 8 days and 6 overnight stays) total.
Informed consent	X											
Inclusion and exclusion criteria	X	X					X					
Demographics	X											
Complete physical examination including height and weight	X											
Abbreviated physical examination		X					X			X	X	
Medical history (includes substance usage and history of renal disease)	X											Substances: drugs, alcohol, and caffeine. Subjects with renal impairment should be on a stable regimen of chronic medications 7 days before the first dose of study drug on Day 1.

Procedure ^a	Screening (up to 30 days prior to Day -1)	Check -in	Treatment Period (Days)								Follow-up (10 [±5] days post-last dose) or Early Termination	Notes	
			1				2						
			-1	1	2	3	4 to 6	7	8	9			10
Past and current medical conditions (including renal impairment medical history and eGFR)	X												eGFR defined in the FDA draft guidance for industry, "Pharmacokinetics in Patients with Impaired Renal Function" [DHHS, 2010].
Serum or urine pregnancy test/FSH	X	X					X					X	Serum (or urine) pregnancy test (if WCBP); estradiol and FSH at Screening as appropriate.
HIV antibody, hepatitis B surface antigen, and hepatitis C antibody testing ^c	X												
Drug and alcohol screen	X	X					X						See Table 6 .
Laboratory assessments (include liver chemistries)	X	X		X			X		X			X	Including serum chemistry, and hematology. Results from 24 hours after dosing should be available before discharge on Day 3 (Period 1) and Day 10 (Period 2)
12-lead ECG	X	X	X	X	X		X	X	X	X		X	
Vital signs	X	X	X	X	X		X	X	X	X		X	Respiratory rate and body temperature collected at Screening only.

Procedure ^a	Screening (up to 30 days prior to Day -1)	Check -in	Treatment Period (Days)								Follow-up (10 [±5] days post-last dose) or Early Termination	Notes	
			1				2						
			-1	1	2	3	4 to 6	7	8	9			10
Genetic sample ^d		X											Collect a pharmacogenomics (PGx) sample only if the subject has a signed consent specific for this purpose. The PGx sample can be collected anytime, but Day -1 is recommended.
Study drug administration			X ^b					X ^b					
Blood collection for pharmacokinetics			X	X	X			X	X	X			See Table 5 for time points.
Urine collection for pharmacokinetics			X	X	X			X	X	X			See Table 5 for time points. Subjects may not be able to produce a urine sample.
Dialysate collections for pharmacokinetics			X	X	X								See Table 5 for time points.
AE/SAE review	X	X	←=====→								X		
Concomitant medication review		X	←=====→					←=====→			X		

Footnotes continued on the next page.

AE = adverse event, eGFR = estimated glomerular filtration rate, ECG = electrocardiogram, FSH = follicle-stimulating hormone; HIV = human immunodeficiency virus, PGx = pharmacogenetic, SAE = serious AE; WCBP = women of childbearing potential.

- a For subjects on hemodialysis (Part 2 [optional], Group F), assessments performed on scheduled hemodialysis days are to be done before hemodialysis (except for PK sample collection, which will be done before and after hemodialysis).
- b Subjects in Group F will participate in 2 treatment periods, with dosing in these periods separated by a washout period of at least 7 days. Subjects in Group F will enter the clinic at Check-in (Day -1, Period 1 and Day 7, Period 2) before each study drug administration (Day 1, Period 1 and Day 8, Period 2). On Day 1 (Period 1) and Day 8 (Period 2), subjects in Group F will receive a single dose of study drug as follows: gepotidacin 750 mg administered as a 2-hour IV infusion starting approximately 2 hours before initiation of the last hemodialysis session of the week (Period 1) and gepotidacin 750 mg administered as a 2-hour IV infusion starting within 2 hours after completion of the last hemodialysis session of the week (Period 2). Subjects in Group F will be discharged from the clinic on Day 10, Period 2.
- c If test has otherwise been performed within 3 months prior to first dose of study treatment, testing at Screening is not required.
- d Informed consent for optional substudies (e.g., genetics research) must be obtained before collecting a sample.

Table 5 Safety and Pharmacokinetic Assessments (Group F)

Procedure ^a	Predose	Treatment Periods 1 and 2															
		Time point (hours) ^a															
		0	0.25	0.5	1	1.5	2	2.5	3	4	6	8	12	24 ^b	36 ^b	48 ^b	
12-lead electrocardiogram	X						X ^c			X		X	X	X	X	X	
Vital signs	X						X ^c			X		X	X	X	X	X	
Treatment administration 2-hour IV gepotidacin infusion ^d		X															
Blood collection for pharmacokinetics	X		X	X	X	X	X	X	X	X	X	X	X	X	X	X	
Urine collection for pharmacokinetics ^e	X	X										X	X	X	X	X	
Dialysate collection for pharmacokinetics ^f	X	X		X		X		X									

^a When coinciding with safety and/or pharmacokinetic assessments, electrocardiograms, vital signs, and pharmacokinetic blood collections should be performed in said order.

^b The 24-, 36-, and 48-hour postdose time points correspond to time points on Day 2 and 3, respectively.

^c Performed post infusion.

^d Subjects in Group F will participate in 2 treatment periods, with dosing in these periods separated by a washout period of at least 7 days. Subjects in Group F will enter the clinic at Check-in (Day -1, Period 1 and Day 7, Period 2) before each study drug administration (Day 1, Period 1 and Day 8, Period 2). On Day 1 (Period 1) and Day 8 (Period 2), subjects in Group F will receive a single dose of study drug as follows: gepotidacin 750 mg administered as a 2-hour IV infusion starting approximately 2 hours before initiation of the last hemodialysis session of the week (Period 1) and gepotidacin 750 mg administered as a 2-hour IV infusion starting within 2 hours after completion of the last hemodialysis session of the week (Period 2). Subjects in Group F will be discharged from the clinic on Day 10, Period 2.

^e It should be noted that subjects in Group F may not be able to produce urine samples due to their medical condition. All sampling times are relative to the start of the infusion.

^f Dialysate fluid will be collected on Day 1 after dosing (Period 1 only) over each 1-hour collection interval of the hemodialysis session.

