9.4. Key Elements of Analysis Plan

9.4.1. Primary Analyses

Pharmacokinetic Analyses

Plasma, urine, and saliva concentrations of gepotidacin will be subjected to PK analyses using noncompartmental methods. Based on the individual concentration time data the following parameters will be estimated:

Plasma:

AUC(0-∞)	Area under the concentration-time curve from time 0 (predose) extrapolated to infinite time
AUC(0-t)	Area under the concentration-time curve from time 0 (predose) to time of last quantifiable concentration
CL	Systemic clearance
C _{max}	Maximum observed concentration
λ _z	Terminal-phase rate constant
t _{1/2}	Terminal phase half life
T _{max}	Time to first occurrence of C _{max}
V _{ss}	Volume of distribution at steady-state of parent drug
V _z	Volume of distribution of the terminal phase

Urine:

A _e total	Total unchanged drug (total amount of drug excreted in urine), calculated by adding all the fractions of drug collected over all the allotted time intervals
A _e (t ₁ -t ₂)	Amount of drug excreted in urine in a time intervals for predose, 0 to 6, 6 to 12, 12 to 24, or 24 to 36, and 36 to 48 hours after dosing for subjects with renal impairment; and predose, 0 to 2 hours, 2 to 4 hours, 4 to 6 hours, 6 to 8 hours, 8 to 12 hours, 12 to 24 hours, 24 to 36 hours, and 36 to 48 hours for subjects with normal renal function
fe%	Percentage of the given dose of drug excreted in urine, calculated as: fe% = (A _e total/Dose) × 100
CL _r	Renal clearance of drug, calculated as: A _e total/AUC(0-t)

Dialysate (Subjects with ESRD on dialysis; Group F subjects in Part 2):

A _{rem} (0-1)	Amount of drug removed by hemodialysis from time 0 to 1 hour after the start of hemodialysis
A _{rem} (1-2)	Amount of drug removed by hemodialysis from time 1 to 2 hours after the start of hemodialysis

Arem(2-3)	Amount of drug removed by hemodialysis from time 2 to 3 hours after the start of hemodialysis
Arem(3-4)	Amount of drug removed by hemodialysis from time 3 to 4 hours after the start of hemodialysis (or to the end of dialysis if less than 4 hours)
Arem(0-4)	Cumulative amount of drug removed by hemodialysis from time 0 to 4 hours after the start of hemodialysis (or to the end of dialysis if less than 4 hours)
AUC(t0-t1)	Partial area under the curve estimated from predialyzer samples collected from start of dialysis (t0) to end of dialysis (t1)

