**Safety and PK Assessments (Groups A, B, C, D, and E)**

Procedure a	Predose	Treatment Period Time point (hours)														
		0	0.25	0.5	1	1.5	2	2.5	3	4	6	8	12	24 b	36 b	48 b
12-lead electrocardiogram	X					X	X			X		X	X	X	X	X
Vital signs	X					X	X			X		X	X	X	X	X
Treatment administration 2-hour IV gepotidacin infusion		X														
Blood collection for pharmacokinetics	X		X	X	X	X	X	X	X	X	X	X	X	X	X	X
Urine collection for pharmacokinetics (subjects with normal renal function) c	X	X					X			X	X	X	X	X	X	
Urine collection for pharmacokinetics (subjects with renal impairment) d	X	X								X		X	X	X	X	
Saliva collections e	X		X	X	X	X	X	X	X	X	X	X	X	X	X	X

- a When coinciding with safety and/or pharmacokinetic assessments, electrocardiograms, vital signs, and pharmacokinetic blood collections should be performed in said order.
- b The 24-, 36-, and 48-hour postdose time points correspond to time points on Day 2 and 3, respectively.
- c Urine collection intervals for subjects with normal renal function (Group A and Group D) include 0 (pre-dose), 0 to 2 hours, 2 to 4 hours, 4 to 6 hours, 6 to 8 hours, 8 to 12 hours, 12 to 24 hours, 24 to 36 hours, and 36 to 48 hours.
- d Urine collection intervals for subjects with renal impairment (Group B, Group C, and Group E) include 0 hour (pre-dose), 0 to 6 hours, 6 to 12 hours, 12 to 24 hours, 24 to 36, and 36 to 48 hours.
- e Subjects in Part 1 only. It should be noted that subjects with renal impairment may be on medications that may prevent saliva collections.

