3.6	PK Parameters	PKPT4	Summary of Gepotidacin Plasma Parameters by Group	Additional parameters include untransformed and log-transformed for AUC(0-t) (units), AUC(0-∞) (units), Cmax (units);only untransformed – Tmax (units), CL (units), t½ (units), Vss (units), Vz (units), and lambda-z (units). Repeat for part 2 if needed.	SAC [1]
3.7	PK Parameters	PKPT1	Summary of Gepotidacin Urine Pharmacokinetic Parameters by Renal Function	Normal Subjects: Ae(0-2), Ae(2-4), Ae(4-6), Ae(6-8), Ae(8-12), Ae(12-24), Ae(24-36), Ae(36-48), Ae total, fe%, Clr, AUC(0-12), AUC(0-24), AUC(0-48) Renal Impaired: Ae(0-6), Ae(6-12), Ae(12-24), Ae(24-36), Ae(36-48), Ae total, fe%, CLr, AUC(0-12), AUC(0-24), AUC(0-48). Repeat for Part 2.	SAC [1]
3.8	PK Parameters	PKPT4	Summary of Gepotidacin Saliva Pharmacokinetic Parameters by Renal Function	AUC(0-t), AUC(0-∞), Cmax; only untransformed – Tmax, CL, t½, Vz, Vss, RAUC(0-t), RAUC(0-∞) and lambda-z. Part 1 subjects only.	SAC [1]
3.9	PK Parameters	PKPT4	Summary of GSK2140944 Dialysate and Dialyzer Parameters by Group	Arem(0-1), Arem(1-2), Arem(2-3), Arem(3-4), Arem(0-4), AUC(t0-t1), CLD, Frem%(0-4). Part 2 Group F only if needed.	SAC [1]

Pharmacokinetic : Tables					
No.	Population	IDSL / TST ID / Example Shell	Title	Programming Notes	Deliverable [Priority]
PK Analysis Tables					
3.10	PK Parameters	PKPT3	ANOVA of Gepotidacin Plasma Pharmacokinetic Parameters by Renal Function	AUC(0-t), AUC(0-∞), Cmax only log-transformed vs eGFR. Repeat for CrCL. Repeat for Part 2.	SAC [1]
3.11	PK Parameters	PK_T1	Linear Regression of Gepotidacin Plasma Pharmacokinetic Parameters by Renal Function	AUC(0-t), AUC(0-∞), Cmax only log-transformed. Repeat for Part 2.	SAC [1]

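### The urine marks for renally impaired subjects in protocol Table 3, repeated in SAP Appendix 1, conflict with footnote d and with the Ae intervals to be reported

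*Protocol*

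**What the plan says.** **Groups B, C and E, in words.** Footnote d of protocol Table 3 gives the intervals: "Urine collection intervals for subjects with renal impairment (Group B, Group C, and Group E) include 0 hour (pre-dose), 0 to 6 hours", followed by 6-12, 12-24, 24-36 and 36-48 h. The endpoint definition in protocol 9.4.1 agrees: "Amount of drug excreted in urine in a time intervals for predose, 0 to 6, 6 to 12". SAP Table 5, the programming note to display 3.2, and Listing 47 carry the same intervals. Display 3.7 in SAP 9.11.6 lists "Renal Impaired: Ae(0-6), Ae(6-12), Ae(12-24), Ae(24-36), Ae(36-48), Ae total, fe%, CLr".

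**Groups B, C and E, as marks.** The row in Table 3 labelled "Urine collection for pharmacokinetics (subjects with renal impairment) ^d" is marked at predose, 0, 4, 8, 12, 24 and 36 h. SAP Appendix 1 reproduces both the row and the footnote.

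**Groups A and D.** Footnote c begins "Urine collection intervals for subjects with normal renal function (Group A and Group D) include 0 (pre-dose), 0 to 2 hours" and continues through 2-4, 4-6, 6-8, 8-12, 12-24, 24-36 and 36-48 h.

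**Group F.** Protocol Table 5 marks urine at predose, 0, 8, 12, 24, 36 and 48 h. Its footnote says "All sampling times are relative to the start of the infusion" but names no intervals. Footnote d and display 3.2 name only Groups B, C and E.

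**The concern.** Protocol Section 7 sends sites to the Time and Events Tables for exact timing, treats adherence to them as required, and allows waivers only for immediate safety concerns. The urine row of Table 2 and Section 7.4.2 point to the same tables. A site arriving there finds a row and a footnote that disagree. The row for normal subjects, just above, does match its footnote, so the site has some reason to trust the marks.

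The study is multi-center, so different sites could resolve the conflict differently. Urine pooled over 4 to 8 h cannot be divided afterwards at 6 h. What is at stake is the first two reported intervals of a secondary endpoint in Groups B and C (about 8 subjects each) and in Group E if enrolled (about 4 to 8), so about 16 to 24 subjects.

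**Working it through.** The plan gives no figure to reproduce here. The check maps each urine row onto the 16 column heads of the table (predose, 0, 0.25, 0.5, 1, 1.5, 2, 2.5, 3, 4, 6, 8, 12, 24, 36, 48 h) and asks which planned intervals can be formed. Ae(a-b) is obtainable only if both a and b are collection boundaries.

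**Step 1: what a mark means.** The normal row is marked at 0, 2, 4, 6, 8, 12, 24 and 36 h, with 48 h blank. These eight marks are the starts of the eight intervals in footnote c, so a mark denotes an interval start.

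**Step 2: boundaries under each version.**

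| Version | Boundaries (h) | 0-6 | 6-12 | 12-24 | 24-36 | 36-48 |
|---|---|---|---|---|---|---|
| Footnote c (A, D) | 0, 2, 4, 6, 8, 12, 24, 36, 48 | by summing | by summing | yes | yes | yes |
| Footnote d (B, C, E) | 0, 6, 12, 24, 36, 48 | yes | yes | yes | yes | yes |
| Impaired row, marks as starts | 0, 4, 8, 12, 24, 36, 48 | no | no | yes | yes | yes |
| Impaired row, marks as ends | 0, 4, 8, 12, 24, 36 | no | no | yes | yes | no |
| Group F row | 0, 8, 12, 24, 36, 48 | no | no | yes | yes | yes |

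The impaired row fails for 0-6 and 6-12 h whichever way the marks are read. The 36-48 h interval is lost only if marks are taken as ends, which is not how the normal row works.

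**Step 3: could text extraction have shifted the row?** Moving the impaired marks after time 0 one column to the right gives 0, 6, 12, 24, 36 and 48 h, exactly the boundaries of footnote d. Three observations argue against a shift:
- The SAP copy has the marks in the same columns.
- The neighbouring rows (ECG, blood, normal urine) align without any shift.
- A shifted row would carry a mark at 48 h, which the normal row does not (the Group F row does).

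None of these excludes a shift without sight of the PDF.

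**Step 4: common intervals.** In Groups A and D, Ae(0-6) = Ae(0-2) + Ae(2-4) + Ae(4-6), and Ae(6-12) = Ae(6-8) + Ae(8-12). The boundaries shared by footnotes c and d and the Group F row are 0, 12, 24, 36 and 48 h. So 0-12, 12-24, 24-36 and 36-48 h can be formed in every group.

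**Step 5: primary urine endpoints.** Ae total is the sum over all collections however they are split, and fe% and CLr derive from it. None needs a 6 h boundary. They would be affected only if a site read marks as ends and omitted 36-48 h.

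**The case against.** The strongest reply is that footnote d defines the intervals in words, sits in the same table, and agrees with every text that defines or reports the endpoint for Groups B, C and E. The one outlier is a row of marks, which may be an extraction artefact. Marks in these tables are not always literal boundaries either. The Group F dialysate row, as extracted, reads predose, 0, 0.5, 1.5 and 2.5 h, although dialysis starts about 2 h after the infusion begins and collections are hourly. This stands as a reason to check the PDF and to treat footnote d as the intended schedule. It does not remove the need to reconcile the row.

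Second, protocol 7.4.2 has actual urine times recorded and SAP 7.1.3.1 bases calculations on actual sampling times, so a 0-4 h container would be recognised. That guards against mislabelling but does not recover Ae(0-6).

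Third, Table 2 says openly that normal and impaired subjects have different intervals, and the normal intervals nest inside those of footnote d. That stands. Comparability before 12 h needs only an addition, although the SAP does not ask for it.

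Fourth, Group F is optional and may yield no urine. Display 3.7 asks for a repeat in Part 2 but does not say that its impaired list covers Group F. The supportable point is that Group F's intervals are undefined.

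**Conclusion.** There is an internal inconsistency, in both documents as extracted, between the impaired urine row and the intervals defined everywhere else. If a site follows the marks, two of the five planned Ae(t1-t2) intervals are lost for its Group B, C and E subjects. If it follows footnote d, none is lost. Group F additionally lacks stated intervals. The conclusion for Groups B, C and E assumes that the columns were extracted correctly; the better reading is that they were.

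A reader might infer that Ae(t1-t2) cannot be computed or compared as planned. The documents do not support that. Footnote d yields all five intervals, the planned summaries are descriptive, and the ANOVA covers only plasma AUC and Cmax. A reader might also want the share of Ae(0-6) that a 0-4 h collection would hold. That needs an elimination rate that neither document states, and the case for correction does not depend on it.

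**What to change.** 1. Check the impaired urine row in the source PDF of both documents. If it reads as extracted, correct protocol Table 3 and SAP Appendix 1 to interval-start marks at predose, 0, 6, 12, 24 and 36 h, the convention of the normal row.
2. State Group F's urine intervals in protocol Table 5 and 9.4.1 and in SAP Table 5 and displays 3.2 and 3.7. Alternatively, limit its summary to 0-12, 12-24, 24-36 and 36-48 h.
3. In display 3.7, add Ae(0-6) and Ae(6-12) for Groups A and D as the sums shown above.
4. If any impaired subject was already collected at the marked times, report that subject on 0-12 h and later intervals, since 0-4, 4-8 and 8-12 h add up to 0-12 h.

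The cost is a table correction and a few lines of SAP text. No samples are added. Under footnote d, Groups B, C and E fill five post-dose collections instead of the six that the marks imply. Items 1 and 2 should reach sites before collection starts; item 3 can be done at any time before reporting.
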